11. PRIOR AND CONCOMITANT MEDICATION, AND OTHER RESTRICTIONS

11.1 Prior Medications

Chronic medications such as antihypertensives, bronchodilators, oral contraceptives or statins that do not affect the immune system, will be permitted and allowed to continue during the study at the discretion of the Investigator.

Non-permitted medications are provided in the exclusion criteria Section 9.2.

11.2 Concomitant Medications

Paracetamol will be permitted for the treatment of headache or other symptomatic pains.

Any medication the subject takes, other than study vaccine and approved medications approved by the PI will be considered a concomitant medication; this will include herbal and other remedies. All concomitant medications taken during the study must be recorded in the CRF.

11.3 Other Restrictions

The Investigator or designee will request that subjects abstain from:

- Donation of blood or blood products for 90 days after the last dose of trial medication.
- Consumption of alcoholic beverages within 24 hours prior and post dosing and scheduled clinic visits.
- Use of cosmetics or creams at the site of vaccination that are known to cause irritation within 24 hours prior to dosing and for the duration of the study.
- Excessive exercise or a significant change in usual exercise habit within 7 days prior to dosing and for 7 days post dosing.

12. STUDY CONDUCT

Please refer to the schedule of assessments (Table I, section 18) for a detailed overview of the study conduct.

12.1 Screening Period

Screening assessments will be performed within 28 days prior to the first study vaccine administration (Day 1). The following assessments will be carried out at the screening visit (Visit 1) after written informed consent has been obtained:

- Inclusion/Exclusion
- Demography
- Medical history
- Physical examination
- Height, weight, body mass index (BMI)
- Vital signs (heart rate, blood pressure, oral temperature and respiration rate)
- 12-lead electrocardiogram (ECG)
- Urinalysis
- Blood samples for haematology and biochemistry
- Blood samples for HIV, hepatitis B and hepatitis C
- Serum pregnancy test for females of child-bearing potential
- Alcohol urine test
- Urine drugs of abuse test Cannabinoids, amphetamines, cocaine, benzodiazepines, opiates and cotinine.
- A review of all medications taken in the previous month

12.2 Treatment Period and Post-Study Period

Subjects will be administered the primary dose of the appropriate dose of GBS-NN/NN2 or placebo according to the cohort and dosing schedule described in section 10.1 at Visit 2 and a second dose will be administered at Visit 6. All cohorts will incorporate sentinel dosing of 2 subjects in each cohort for the primary dose only: 1 on active treatment and 1 on placebo. No further subjects in that cohort will be dosed until 24 hours after dosing the second subject, provided that there are no serious or unexplained safety issues as determined by the Investigator.

The decision to proceed with administration of the primary dose in the subsequent cohort will be made as described in Section 12.5.

The following assessments will be carried out at these visits:

Visit 2

A general medical review, vital signs, urine pregnancy test, urine drugs of abuse test and alcohol urine test will be performed to re-confirm eligibility. Eligible subjects will then be randomised to receive the appropriate treatment as per the randomisation list for the cohort. A pharmacodynamic blood sample will be taken to measure pre-existing antibody levels and to obtain Peripheral Blood Mononuclear Cells (PBMCs) to assess cellular responses, prior to

dosing. Blood sample for haematology and serum biochemistry will be taken. Vital signs will be recorded at pre-dose (within 60 minutes of dosing), 2 (± 0.25) and 4 (± 0.25) hours post-dose. A general medical examination (including an assessment of the injection site) will be performed prior to discharge to ensure the subject is fit for discharge. At discharge subjects will be provided with oral temperature kit and instructed to record a temperature if they feel unwell in the seven days post dose.

Visit 3

Visit 3 will be performed 24 hours (± 2 hours) after administration of the primary dose and an assessment of the injection site will be performed, vital signs will be recorded and AEs and concomitant medications will be reviewed.

Visit 4

Visit 4 will be performed 1 week (± 1 day) after administration of the primary dose. An assessment of the injection site will be performed, vital signs will be recorded, safety blood samples for haematology and biochemistry will be collected, urinalysis will be performed and AEs and concomitant medications will be reviewed.

Visit 5

Visit 5 will be performed 2 weeks (± 2 days) after administration of the primary dose. This visit will review of AEs and concomitant medications. An assessment of the injection site will be performed, vital signs will be recorded, safety blood samples for haematology and biochemistry will be collected and a pharmacodynamic blood sample will be taken to measure the antibody response.

Visit 6

Visit 6 will be performed 4 weeks (± 3 days) after Visit 2. An assessment of the injection site, AEs and concomitant medications review, urine pregnancy test, and a pharmacodynamic blood sample will be taken to measure the antibody response prior to administering the second dose. Vital signs will be recorded pre-dose and at 2 (± 0.25) and 4 (± 0.25) hours post-dose. A brief medical examination (including an assessment of the injection sites) will be performed prior to discharge to ensure the subject is fit for discharge. At discharge subjects will be provided with oral temperature kit and instructed to record a temperature if they feel unwell in the 7 days post dose.

Visit 7

Visit 7 will be performed 24 hours (± 2 hours) after administration of the booster dose and an assessment of the injection sites will be performed, vital signs will be recorded and AEs and concomitant medications will be reviewed.

Visit 8

Visit 8 will be performed 2 weeks (± 2 days) following Visit 6 and the following assessments will be performed: an assessment of the injection sites, vital signs will be recorded, safety blood samples for haematology and biochemistry will be collected, urinalysis will be performed, a pharmacodynamic blood sample will be taken to measure antibody response and to obtain PBMCs to assess cellular responses, and AEs and concomitant medications will be reviewed.

Visit 9

Visit 9 will be performed 8 weeks (± 2 days) following the first study vaccine administration and the following assessments will be performed: an assessment of the injection site and a pharmacodynamic blood sample will be taken to measure antibody response and AEs and concomitant medications will be reviewed.

Visit 10

A full medical examination will be performed 12 weeks (Day 85±2 days) following the first study vaccine administration and the following assessments will be carried out: an assessment of the injection site, a pharmacodynamic blood sample will be taken to measure antibody response, physical examination, vital signs, urinalysis, blood samples for haematology and biochemistry, serum pregnancy test and a review of AEs and concomitant medications. This visit signifies the endpoint for the primary endpoint for the study.

Safety Follow-Up (Visit 11)

A safety follow-up visit will be performed 6 months (±2 weeks) following the second study vaccine administration to check the general health, measure vital signs, collect blood for haematology, biochemistry and to assess the immune response of the subject and to review adverse events (AEs).

Subjects do not have to use highly effective contraception following the Day 85 visit, should any subject become pregnant between Day 85 and Day 210, permission will be sought to follow the pregnancy, to obtain data on the outcome of the pregnancy.

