6.3 Risk/Benefit Assessment

Antibodies against the full-length Rib, AlphaC, Alp1, Alp2 and Alp3 proteins, from which the GBS-NN and GBS-NN2 are derived to make up the vaccine antigens, naturally occur in women exposed to GBS, and such antibodies are efficiently transferred to the unborn child *in-utero*. Many adults and new-born infants have, therefore, already been naturally exposed to the proteins from which the antigen is derived and to antibodies against these proteins, and no side effects have been attributed as a consequence of such exposure in humans.

[REDACTED]

[REDACTED]. The maximum human dose will be 50 µg, which if administered to a 60 kg woman would equate to 0.83 µg/kg giving a safety margin of at least 60-fold.

The planned excipients in the vaccine formulation are also all well-known from other vaccines, and no novel or non-tested components are used. The proteins in the vaccine are adsorbed with a known adjuvant, Alhydrogel®, (0.5 mg of Al³⁺ per dose), corresponding to the dose used in many other commercial vaccines.

This is a new investigational product; therefore, there are currently no expected AEs related to the product. However, following injection of GBS-NN alone, approximately 30% of the subjects in the study experienced mild pain. Pain post-injection that is worse than mild would be considered to be unexpected. It is not anticipated that adding the two additional antigenic proteins, to GBS-NN, bound to Alum will significantly alter the safety profile. The Investigator is responsible for reporting adverse events (AEs) that occur during the course of the study. Serious adverse reactions that are deemed to be related to the investigational product in the proposed study will be reported as suspected unexpected serious adverse events (SUSAR).

GBS-NN/NN2, like other protein-based vaccines, may theoretically be associated with a transient febrile reaction (body temperature greater than 38.0°C but not greater than 38.7°C) following vaccination. Immune complex-mediated reactions are unlikely given the recombinant nature of GBS-NN/NN2, however, it is still possible that hypersensitivity may occur.

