10.3 Randomisation

Subjects will be randomised pre-dose on the morning of Day 1, once all eligibility criteria have been verified. A randomisation list will be held on site, which will be accessible only to unblinded study personnel.

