12.5 Safety Monitoring Board and Safety Data Review Meetings

Both cohorts will incorporate sentinel dosing of 2 subjects in each cohort for the primary dose only: 1 on active treatment and 1 on placebo. No further subjects in that cohort will be

dosed until 24 hours after dosing the second subject, provided that there are no serious or unexplained safety issues as determined by the Investigator.

The decision to proceed with administration of the primary dose the subsequent cohort will be made as follows:

- It is intended that safety will be assessed after at least 24 evaluable subjects in cohort 1 (sentinel and main dose groups) have completed Visit 4 (Day 8), at which point the decision will be made to proceed with administration of the primary dose in cohort 2.

At least 24 evaluable subjects are required to complete through to visit 4 in cohort 1, in order to provide sufficient data for a decision to dose escalate. If the required number of evaluable subjects is not obtained in cohort 1, then the safety review committee (SRC) must decide whether there is enough information present to make a decision or whether further subjects should replace the dropped subjects or if sufficient information exists to determine if the dosing of cohort 2 is appropriate. The decision of the safety monitoring board and the output of the safety review must be clearly documented after the meeting.

The following safety data will be reviewed:

- Clinical Laboratory Tests
- Vital signs
- Assessment of injection site reactions
- AEs

The SRC will include at least two voting members - the Principal Investigator and Sponsor's Medical Monitor. If a voting member is unable to attend a Safety Data Review Meeting, a designated back-up can attend on their behalf and act as a voting member. Designated back-ups must be agreed and documented in advance. Non-voting members may also be part of the SRC.

The SRC will meet in person or by teleconference at scheduled Safety Data Review Meetings at which the safety data will be reviewed. A summary of safety data will be provided for review prior to these meetings for the SRC to review.

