12.6 Individual Subject Stopping Criteria

Subjects who meet one or more of the following stopping criteria will receive no further doses of the study vaccine but will be followed up for safety:

- Severe injection site reaction, see Appendix I
- Severe systemic reaction, e.g. anaphylaxis, see section 14.2.1
- Persistent febrile reaction ($\geq 38.5^{\circ}\text{C}$ for ≥ 12 hours) at the Investigator's discretion
- SAE related to the study agent

The medical safety of the subject is of paramount importance when discussing study continuation.

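### The fever stopping rules need about 38.5 °C for 12 hours, but the protocol requires no timed or repeated home temperatures to show it

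*Combined protocol and SAP*

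**What the plan says.** **The rules.** Section 12.6 withholds further doses from a subject with a "Persistent febrile reaction", set at 38.5 °C or higher for 12 hours or more, at the Investigator's discretion. Section 12.7 convenes a Safety Review Meeting if one sentinel, or more than 20% of a cohort, has a vaccine-related fever above 38.5 °C for 12 hours or more. Section 12.5 adds that escalation stops if a Section 12.7 criterion is met.

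**The temperatures.** Oral temperature is one of the vital signs. Under Section 12.2 and Table 1 (Section 18) it is taken before each dose, at 2 h and 4 h, and at 24 h. The next clinic reading is nominally Day 8 after dose 1 and Day 43 after dose 2. At discharge subjects get an oral temperature kit. After dose 1 they are "instructed to record a temperature if they feel unwell in the seven days post dose"; after dose 2 they are "instructed to record a temperature if they feel unwell in the 7 days post dose". Sections 14.1 and 14.3 mention a diary card only after Visit 10.

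**The decisions.** After the two sentinels, nobody else in the cohort is dosed "until 24 hours after dosing the second subject, provided that there are no serious or unexplained safety issues as determined by the Investigator". For the safety review committee, Section 12.5 states "The following safety data will be reviewed" and lists laboratory tests, vital signs, injection-site assessments and AEs.

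**Context.** Section 6.3 says the vaccine "may theoretically be associated with a transient febrile reaction", described as above 38.0 °C and not above 38.7 °C. Section 11.2 states: "Paracetamol will be permitted for the treatment of headache or other symptomatic pains".

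**The concern.** A criterion of 12 hours can be shown only by at least two readings whose times are known. The protocol requires none outside the clinic, and the first night after dosing is the longest stretch without a clinic temperature in the first 24 hours.

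Two decisions depend on this after dose 1: releasing the rest of a cohort after the sentinels, and giving an individual her second dose. The two triggers in Section 12.7 apply after either dose. The fever range in Section 6.3 overlaps the stopping threshold between 38.5 and 38.7 °C. There, temperature alone cannot separate an anticipated transient fever from a persistent one, so duration carries much of the weight.

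The analysis is also unclear. After vaccination, Section 15.1.1 uses scheduled values only, and the vital-sign times in Section 15.4.2 include no home readings. Their place in the tolerability summaries is therefore not set.

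**Working it through.** The plan gives no figure of its own here. The check compares the clinic schedule with the 12-hour criterion.

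**Inputs.** Last dosing-day temperature 4 h ± 0.25 h and next visit 24 h ± 2 h (Sections 12.2 and 12.4); criterion 12 h (Sections 12.6 and 12.7); cohort of 30, of whom 24 receive vaccine (synopsis, study design).

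**Gap between clinic temperatures**
- Nominal: 24 − 4 = 20 h.
- Shortest: (24 − 2) − (4 + 0.25) = 17.75 h.
- Longest: (24 + 2) − (4 − 0.25) = 22.25 h.

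**Onset times that hide a 12-hour fever from both readings**
- Nominal: 20 − 12 = 8 h, that is, onset from 4 to 12 h after the dose.
- With windows: 17.75 − 12 = 5.75 h to 22.25 − 12 = 10.25 h wide.

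Section 10.3 states "Subjects will be randomised pre-dose on the morning of Day 1". If dosing follows that morning, the gap spans the first night.

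**After the 24 h visit.** The next nominal clinic temperature is 8 − 2 = 6 days later after dose 1 and 43 − 30 = 13 days later after dose 2.

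**Sentinel release.** The hold ends 24 h after the second sentinel's dose, but her 24 h visit may fall as late as 26 h. Release can precede that reading by up to 26 − 24 = 2 h.

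**Cohort trigger.** 20% of 30 is 6, so more than 20% means at least 7. If all 7 are vaccinees, that is 7/24 = 29%.

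**What readings can establish.** Assumptions: dose at 09:00; clinic readings below the threshold at 13:00 and at 09:00 next day; high means 38.5 °C or above. The shortest duration runs from the first to the last consecutive high reading. The longest runs between the lower readings on either side. The middle column further assumes that the subject takes exactly one home reading and it is high. The protocol does not limit her to one; it only does not ask for more. The last column uses timed readings at 19:00, 23:00 and 07:00.

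| True fever | One home reading | Timed readings |
|---|---|---|
| 18:30–20:00 (1.5 h) | 0 to 20 h | 0 to 10 h (13:00–23:00): rule not met |
| 17:00–05:00 (12 h) | 0 to 20 h | 4 h (19:00–23:00) to 18 h (13:00–07:00): Investigator judges |
| 17:00–08:00 (15 h) | 0 to 20 h | 12 h (19:00–07:00) to 20 h (13:00–09:00): rule met |

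**Why the shortest duration should not be the rule.** With evenly spaced readings and a random start, a true 14 h fever shows 12 h from first to last high reading with probability 0.50 at 4-hourly and 0.33 at 6-hourly readings. For a true 16 h fever the values are 1.00 and 0.67.

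**The case against.** The strongest reply is that the plan has several other ways to notice a febrile subject. Someone at 38.5 °C for 12 hours would probably feel unwell, which is what prompts the home reading. AEs are to be reported as soon as possible (Section 14.3), and unscheduled assessments are allowed (Section 12.3). Sentinel release uses a broader test with no 12-hour element. The rules on severe systemic reactions, related SAEs and two or more severe reactions do not use fever duration. The dose 2 decision comes about four weeks later, after AE review at Visits 3 to 6, and the AE listing carries duration. All of this stands and limits the consequence. None of it requires a timed temperature, and the Investigator's discretion still needs evidence to work on.

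A reader might infer more than the documents support:
- *That home readings are untimed and duration is pure recall.* The protocol is silent on timing. Kit instructions may add it, and a recorded reading is not recall.
- *That duration alone separates a transient fever from a stopping event.* Section 12.6 also leaves room for discretion. Section 12.7 also needs relatedness, and either a sentinel case or more than 20% of the cohort.
- *That the sentinel trigger lapses after dose 1.* Only the sentinel hold is limited to the primary dose; Section 12.7 sets no such limit.
- *That home readings are barred from analysis.* The scheduled-values sentence in Section 15.1.1 follows one about re-checked values, and Section 15 leaves detail to the SAP. Their use is undefined, not excluded.

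**Conclusion.** The point holds as a mismatch between a criterion and the data required to judge it. The protocol sets a 12-hour fever rule and requires no reading that would show whether it was met during a clinic gap of about 20 h (17.75 to 22.25 h). It does not follow that stopping events will be missed. The documents give no fever rate, onset pattern or reporting rate, so no such probability can be calculated.

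The gap and the trigger count come directly from the protocol. The worked durations rest on the assumed dose time, normal clinic readings and, for the current plan, a single home reading. A subject who took and timed more readings unprompted would narrow the bounds. Confidence is medium, because instructions outside the protocol may already supply timing. The change is still worth making, because it is cheap and bears on the sentinel, dose 2 and committee decisions.

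**What to change.** In Section 12.2, for each dose:
- Use the kit already issued for timed morning and evening readings for 7 days, starting on the evening of dosing.
- If a reading is 38.0 °C or higher, or the subject feels unwell, repeat about every 4 to 6 hours while awake and on waking, until below 38.0 °C.
- Record any paracetamol with its time.

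Record values and times in the eCRF. Give the shortest and longest duration consistent with the readings to the Investigator (for sentinels, before the rest of the cohort is dosed) and to the safety review committee. The Investigator decides whether 12 hours was met. Strict first-to-last counting should not be the rule, because one paracetamol-lowered reading or the overnight gap would understate duration.

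List the fixed readings as scheduled assessments in Section 15.4.2. As a minor correction, use the same sign at 38.5 °C in Sections 12.6 and 12.7; the first now includes that value and the second excludes it.

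Cost: one subject instruction, one eCRF form and about 2 × 7 = 14 fixed readings per dose, plus repeats during fever. The overnight gap is narrowed, not removed.

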12.3 Safety Assessments

The description of safety assessments is given below, and the timings of these assessments is given in the Schedule of Assessments. The time points of the safety assessments may change depending on information gained throughout the study, however the total number of safety assessments per subject will not be reduced, although unscheduled assessments may be performed at the discretion of the Investigator.

12.3.1 Clinical Laboratory Tests

The following parameters will be measured:

Haematology

Red blood cell count

Haemoglobin

Haematocrit

Platelet count

White blood cell count with absolute differential (neutrophils, lymphocytes, monocytes, eosinophils, basophils) counts

Biochemistry

Sodium

Potassium

Chloride

Bicarbonate

Blood urea

Creatinine

Creatine Kinase

Glucose

Calcium

Albumin

Cholesterol

C- reactive protein CRP

Triglycerides

Phosphorus (inorganic phosphate)

Lactate dehydrogenase (LDH)

Total protein
Globulin
Uric acid
Alkaline phosphatase (ALP)
Aspartate aminotransferase (AST)
Alanine aminotransferase (ALT)
Gamma-glutamyl-transferase (GGT)
Total bilirubin
Direct bilirubin

Urinalysis

Specific gravity
pH
Protein
Glucose
Ketone
Occult blood
Leukocyte esterase
Nitrites

Additional urine microscopy analysis will be undertaken, if any abnormalities are detected, to analyse for red blood cells, white blood cells, epithelial cells, bacteria, casts, and crystals.

12.3.2 ECGs and Vital Signs

Screening ECGs will be recorded after the subject has been lying for at least 5 minutes.

Vital signs will be recorded in the supine position, after the subject has been lying for at least 5 minutes. The normal ranges for vital signs are:

Systolic blood pressure	90-140 mmHg
Diastolic blood pressure	40-90 mmHg
Pulse rate	40-100 bpm
Respiration rate	10-20 breaths per minute
Temperature	≥35.8°C and ≤37.5°C

